7.4.2.8 Relationship between Baseline MUBADA SUVr and Cognitive Change

This exploratory analysis will test whether a relationship exists between baseline MUBADA SUVr and cognitive CFB, as measure by both MMSE and CDR-SB.

Partial correlation coefficient (ρ) adjusted for age and baseline cognitive score, will be calculated to assess the relationship between baseline MUBADA SUVr and each

cognitive score CFB. The results will be summarized in a table along with p-values associated with the hypothesis that $p = 0$.

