6.11 MULTIPLE COMPARISONS/MULTIPLICITY

No multiple comparisons/multiplicity adjustment is planned. Unless otherwise specified, hypothesis testing will be two-sided with type I error rate of 0.05.

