7.1.3 Efficacy Population

The efficacy population used in the primary analysis will include all subjects in the safety population with a valid interpretable baseline PET image (SUVr and/or visual read) available. The exploratory efficacy population will include all subjects with available SUVr, flortaucipir visual read, and the relevant clinical/cognitive assessment.

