7.4.2.1 Two-way ANOVA for Comparison of MUBADA SUVr between Amyloid Groups

Depending on available data, the same analyses as described in Section 7.4.1.1 will be performed with the substitution of comparing MUBADA SUVr between amyloid groups (A β + vs. A β -) rather than cognitive groups, via properly set up contrasts.

7.4.2.2 ANCOVA for Comparison of MMSE CFB as a Function of Tau Scan Visual Interpretation

The objective of this analysis is to determine if baseline tau status will predict subjects' cognitive deterioration.

The first hypothesis will test whether a difference in MMSE CFB exists between AD++ and Non-AD++ (AD- and AD+ only) subjects at 12 month follow-up visit.

The second hypothesis will test whether a difference in MMSE CFB exists between subjects with AD pattern (AD+ and AD++) and AD- subjects.

The third hypothesis will test whether a difference in MMSE CFB exists between AD++ and AD- subjects.

Depending on available data, an ANCOVA model with MMSE CFB at 12 months as the dependent variable, adjusted for baseline MMSE, age, cognitive group, level of education, and the interaction of cognitive group and tau status will be used to test these hypotheses. The appropriate contrasts will be set up to test each hypothesis.

Descriptive summary statistics for MMSE at baseline, 12 months and CFB will be summarized for all subjects by tau status (AD-, AD+, AD++). Group LSM, the difference in LSM between groups, and the p-values from each ANCOVA contrast will be included in the table.

A scatter plot will be created to display the relationship between MMSE CFB and baseline MUBADA SUVr across each tau group.

7.4.2.3 ANCOVA for Comparison of CDR-SB CFB as a Function of Tau Scan Visual Interpretation

The same analyses as described in Section 7.4.2.2 will be performed with the substitution of CDR-SB for MMSE.

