7.4.2.9 Relationship between MUBADA SUVr Change and Cognitive Change

Based on data availability, the same analyses as described in Section 7.4.2.9 will be performed with the addition of partial ρ being adjusted for age.

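### The tau–cognitive-change correlations in SAP 7.4.2.8 and 7.4.2.9 pool all diagnoses without adjusting for diagnosis, so they cannot show that tau relates to decline beyond clinical stage

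*SAP*

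**What the plan says.** SAP 7.4.2.8 states its aim as follows: "This exploratory analysis will test whether a relationship exists between baseline MUBADA SUVr and cognitive CFB, as measure by both MMSE and CDR-SB". The statistic is a partial correlation coefficient, "adjusted for age and baseline cognitive score, will be calculated to assess the relationship between baseline MUBADA SUVr" and the change in each cognitive score, reported with a p-value for zero correlation. No stratification by diagnosis is stated. Under SAP 7.1.3, "The exploratory efficacy population will include all subjects with available SUVr, flortaucipir visual read, and the relevant clinical/cognitive assessment", so pooling over AD, MCI, SMC and CN is the natural reading, although the SAP does not say it outright.

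SAP 7.4.2.9 relates SUVr change to cognitive change. It says "the same analyses as described in Section 7.4.2.9 will be performed with the addition of partial" correlation being adjusted for age. It therefore cites its own section number and adds an adjustment that 7.4.2.8 already has.

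For the same MMSE outcome and the visual tau read, the ANCOVA in SAP 7.4.2.2 is "adjusted for baseline MMSE, age, cognitive group, level of education, and the interaction of cognitive group and tau status". SAP 7.4.2.3 repeats this for CDR-SB. SAP 6.8 sets covariates for the ANCOVA and log-linear models but none for the partial correlations. Under SAP 6.11, "hypothesis testing will be two-sided with type I error rate of 0.05", and "No multiple comparisons/multiplicity adjustment is planned".

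**The concern.** The SAP itself treats both halves of the possible confounding as live questions. Section 7.4.1.1 tests whether SUVr differs by cognitive group, and 7.4.2.4 tests whether MMSE change differs between impaired and SMC subjects. If both differences exist, diagnosis is linked to both variables being correlated. Baseline MMSE or CDR-SB stands in for diagnosis only partly, so some of the between-diagnosis gap stays in the partial correlation.

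The size of that gap also depends on the case mix, which the protocol synopsis sets by enrolment targets (about 25 CN, 50 SMC, 25 MCI and 20 AD). The objective stated in 7.4.2.2 is whether baseline tau predicts deterioration. A significant correlation printed next to those results is likely to be read the same way, when it may only restate that the clinically worse groups have more tau and decline faster.

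**Working it through.** **Figure to reproduce.** None. The documents give no power, expected correlation, SUVr, MMSE or change values, and SAP 3.3 says the sample size was not set on statistical grounds. Only the group sizes can be checked: 25 + 25 + 25 + 25 + 20 = 120.

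**The test.** With n subjects and k partialled-out covariates, t = r·√(df/(1 − r²)) with df = n − 2 − k. Two-sided 5% significance needs |r| above t*/√(df + t*²).
- As planned (n = 120, k = 2): df = 116, t* = 1.981, threshold |r| = 0.181.
- With diagnosis added (3 indicator terms, k = 5): df = 113, t* = 1.981, threshold |r| = 0.183.

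**Hand calculation before any adjustment.** Assumed, not in the documents: mean SUVr 1.00/1.03/1.15/1.35 in CN/SMC/MCI/AD; mean 12-month MMSE change 0/0/−1/−2; within-group SD of change 2; within-group SUVr SD 0.1 or 0.2; no relation within any group. Weights are 25/50/25/20 out of 120.
- Mean SUVr = 132.25/120 = 1.102. Mean change = −65/120 = −0.542.
- Between-group covariance = −82.75/120 − (1.102)(−0.542) = −0.0926.
- Between-group variance: SUVr 0.0151, change 0.582.
- SUVr SD 0.2: r = −0.0926/[√(0.0151 + 0.04)·√(0.582 + 4)] = −0.18.
- SUVr SD 0.1: r = −0.0926/[√(0.0151 + 0.01)·√(0.582 + 4)] = −0.27.

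Group means alone thus give a raw correlation at or beyond the 0.181 threshold. The next question is how much of it the baseline score removes.

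**Simulation with the planned adjustment.** There were 2,000 runs per scenario, with tau and MMSE change independent within each diagnosis. N was 120, or 96 (80% of each group, since SAP 6.9 neither replaces nor imputes dropouts). Further assumptions: mean baseline MMSE 29/28.7/27/22 (strong proxy for diagnosis) or 28.8/28.6/27.5/25 (weak proxy); SUVr SD 0.1, 0.2 or rising from 0.08 to 0.30 by group; SD of change 2, or rising from 1.2 to 3 by group.

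| Mean MMSE change, MCI/AD | Rejection as planned | Mean partial r |
|---|---|---|
| 0/0 | 4–6% with equal SD of change; up to 16% otherwise | about 0 |
| −0.5/−1 (small) | 6–32% | −0.04 to −0.12 |
| −1/−2 (moderate) | 12–66% | −0.08 to −0.23 |
| −1.5/−3 (large) | 19–91% | −0.11 to −0.32 |

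Low ends occur where baseline MMSE is a strong proxy for diagnosis, high ends where it is a weak one.

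**With cognitive group added.** Mean partial r is about 0.00 in every scenario and rejection is 4–6%. The exception is when the SDs of both SUVr and change rise with severity: the MMSE simulations run for this point then leave about 12–17%.

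**Sensitivity cost.** In one scenario with a true within-diagnosis correlation of −0.3 and N = 120, the adjusted test rejected in 91% of runs, against 98% without diagnosis.

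**CDR-SB and SUVr change.** A separate check on CDR-SB change, also with assumed inputs and no within-group relation, gave 10–82% rejection as planned. With both SDs rising with severity, 20–23% remained after adjustment. The SUVr-change correlation in 7.4.2.9 was not simulated, so no size is claimed for it.

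**The case against.** The strongest reply is that 7.4.2.8 asks only whether a relationship exists given age and baseline score. In the simulated settings with group differences in decline, that correlation really is non-zero, so the rejections are not false positives for the hypothesis as worded. The study goal in the protocol and SAP introductions is to look across the AD spectrum, and the third exploratory objective does not condition on diagnosis. The protocol introduction presents tau as a possible marker of severity, so diagnosis may lie partly on the path from tau to decline, and adjusting for it could remove real signal. All of this stands. It is why the pooled coefficient should be kept and not replaced.

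Two consistency points also stand. The log-linear models in 7.4.2.6 and 7.4.2.7 omit cognitive group too, so the omission is not peculiar to the correlations. And 7.4.2.2 and 7.4.2.3 already give a diagnosis-adjusted answer for the visual read. They do not give one for quantitative SUVr, though, and the SAP does not say the correlations are meant as across-spectrum description only.

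A reader might infer that group differences by themselves will make these correlations significant. The documents do not support that: they contain no SUVr or decline figures, the SUVr difference between groups is a hypothesis still to be tested, and with small differences and a strong baseline proxy the rejection rate is close to nominal. A reader might also infer from the circular reference that 7.4.2.9 has no usable definition. It evidently means 7.4.2.8, so this is mainly an editorial slip, although the covariate list still has to be written down.

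**Conclusion.** The concern holds in a conditional form. The planned correlations leave out diagnosis. If tau and rate of decline both differ by diagnosis, they can be significant with no relation inside any diagnosis. The size cannot be fixed from the documents: for baseline SUVr and MMSE change, it runs from about 6% to about 90% rejection at a nominal 5%, depending on the assumed group differences in decline, the SUVr spread and how well the baseline score stands in for diagnosis. The direction carries over to CDR-SB on assumed inputs.

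The pooled coefficient is a valid description across the spectrum. It is not evidence that tau predicts or tracks decline beyond clinical stage, and with unadjusted 0.05 testing the SAP has nothing to stop it being read that way. Only exploratory analyses are touched. This is a cheap improvement to interpretability, not a threat to the study's main conclusion.

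**What to change.** In SAP 7.4.2.8 and 7.4.2.9:

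1. Keep the pooled partial correlation, labelled as across-spectrum and descriptive.
2. Report beside it a partial correlation that also adjusts for cognitive group (AD, MCI, SMC, CN), and the coefficients in impaired (AD and MCI) and unimpaired (SMC and CN) subjects separately.
3. Base any statement that tau predicts or tracks decline on the diagnosis-adjusted value.
4. Use a heteroscedasticity-robust p-value or one from permutation within diagnosis, because adjustment alone leaves excess rejection when variances grow with severity.
5. In 7.4.2.9, refer to 7.4.2.8 and list the covariates in full, stating whether baseline SUVr is one of them (SAP 6.8 requires it for ANCOVAs of SUVr change but is silent on correlations).

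The cost is a wording change using data already collected. Adding diagnosis takes 3 degrees of freedom (116 to 113 at N = 120) and some sensitivity (98% to 91% in the one scenario examined). If diagnosis is partly a consequence of tau, the adjusted value will understate the total association, so the two figures should be read together.

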7.4.2.9 Relationship between MUBADA SUVr Change and Cognitive Change

Based on data availability, the same analyses as described in Section 7.4.2.9 will be performed with the addition of partial ρ being adjusted for age.

7.4.2.10 Comparison of MUBADA SUVr CFB as a Function of Amyloid Status

The hypothesis for testing is whether MUBADA CFB within each amyloid group (AB+ and AB-) is equal to 0.

Descriptive summary statistics for MUBADA SUVr at baseline, 12 months and CFB will be summarized for all subjects by amyloid status (A β + and A β -). Paired t-tests will be run for each group separately and the p-values from each test will be included in the table.

Box-and-whisker plots will be generated to visualize MUBADA CFB across amyloid groups.

7.5 ANALYSIS OF SAFETY

7.5.1 Exposure

The total dose administered of flortaucipir will be summarized using megabecquerels (MBq) in a table using descriptive statistics by imaging visits and collectively. Exposure data captured on the CRF will be presented in a listing.

7.5.1.1 Unit Conversion and Volume Calculation

All exposure tables will display volume in MBq. Radioactive dose collected in millcuries (mCi) will be converted to MBq as follows:

$$MBq = 37 \times mCi$$

7.5.2 Flortaucipir PET Scan

Imaging information captured on the CRF during the flortaucipir imaging visits will be presented in a listing for the safety population.

7.5.3 Treatment Emergent Adverse Events

A summary of TEAEs will be reported in the tables including number of all TEAE and number of subjects with at least one TEAE. The summary of TEAEs will be broken down

further in descending frequency by SOC and PT, and by PT only in separate tables. A subject will be counted once if the subject reported one or more events in a given level of summarization.

All TEAEs will be presented in a listing for the safety population.

7.5.4 Severity

TEAE severity will be reported in a table in the same manner as outlined in 7.5.3. If a subject reported more than one TEAE with the same SOC or PT, the highest severity level will used.

7.5.5 Serious Adverse Events

Serious TEAEs will be summarized in a similar manner as described in Section 7.5.3. If a subject reported more than one serious TEAE with the same SOC or PT, the TEAE will be counted only once in that SOC or PT.

7.5.6 Adverse Events Leading to Study Discontinuation

TEAEs leading to study discontinuation will be summarized in a similar manner as described in section 7.5.3.

7.5.7 Adverse Events Leading to Death

TEAEs leading to death will be summarized in a similar manner as described in section 7.5.3.

7.5.8 Missing and Partial AE Onset Dates

See appendix 1.1 for specific algorithms to impute missing start and stop dates.

7.5.9 Analysis of Vital Signs

Supine blood pressure, pulse rate, and respiratory rate will be monitored for significant changes at the flortaucipir imaging visits.

Immediately Prior to Injection (within 5 minutes) will be considered the baseline value for all change calculations of systolic and diastolic blood pressures, pulse rate, and respiratory rate.

The data from each visit (Screening, Initial Flortaucipir Imaging, and 12 Month Flortaucipir Imaging) along with calculated CFB, defined as the difference from the *Prior to Injection* to *Prior to Discharge* values at the each imaging visits, will be summarized in aggregate. A paired t-test will be performed of each vital sign to assess if any significant changes occurred.

Vital signs and changes (where applicable) will be presented in a listing for the safety population.

7.5.10 Potentially Clinically Significant Vital Sign Changes

Vital signs will be monitored for potentially clinical significance (PCS). Below are the PCS criteria.

Table 3: Potentially Clinical Significant Criteria

Vital Sign		PCS Criteria	
		Low	High
Systolic blood pressure	mmHg	≤ 90 and ≥ 20 decrease	≥ 180 and ≥ 20 increase
Diastolic blood pressure	mmHg	≤ 50 and ≥ 15 decrease	≥ 105 and ≥ 15 increase
Pulse rate	bpm	≤ 50 and ≥ 15 decrease	≥ 120 and ≥ 15 increase

Respiration rate	Breaths/min	≤ 10	
------------------	-------------	------	--

7.5.11 Follow-up Telephone Contact Data

The follow-up contact information captured on the CRF will be presented in a listing for the safety population.

APPENDIX I: ALGORITHMS TO HANDLE MISSING AND PARTIAL DATES

1.1. MISSING AND PARTIAL AE ONSET AND END DATES

If the AE onset dates are missing, then the most conservative approach will be used to decide if the AE is TEAE or not, as detailed in the table below:

AE ONSET DATE/TIME	AE STOP DATE/TIME	ACTION
Partial, but known components show that it cannot be on or after an injection date/time and within 48 hours post-injection	Known	Not TEAE
	Partial	Not TEAE
	Missing	Not TEAE
Partial, could be on or after an injection date/time and within 48 hours post-injection	Known	If stop date/time < flortaucipir injection date/time, then not TEAE If stop date/time >= flortaucipir injection date/time, then TEAE
	Partial	Impute stop date as latest possible date (i.e. 59 if minutes unknown or 23:59 if hours and minutes unknown; last day of month if day unknown or 31st December if day and month unknown), then: If stop date/time < flortaucipir injection date/time, then not TEAE If stop date/time >= flortaucipir injection date/time, then TEAE
	Missing	Assumed TEAE
Missing	Known	If stop date/time < flortaucipir injection date/time, then not TEAE If stop date/time >= flortaucipir injection date/time, then TEAE
	Partial	Impute stop date as latest possible date (i.e. 59 if minutes unknown or 23:59 if hours and minutes unknown; last day of month if day unknown or 31st

AE ONSET DATE/TIME	AE STOP DATE/TIME	ACTION
		December if day and month unknown), then: If stop date/time < flortaucipir injection date/time, then not TEAE If stop date/time \geq flortaucipir injection date/time, then TEAE
Missing		Assumed TEAE

For the summarization of TEAEs by intensity, events recorded with missing intensity will be summarized as Severe.

For the summarization of TEAEs by seriousness, events recorded with missing seriousness will be summarized as Serious.

For the summarization of TEAEs by relationship to study drug or protocol procedure, events recorded with missing relationship will be summarized as Related.
